**Safety and Feasibility of Single Port Robot in Colorectal Procedures**

**NCT: Unavailable at this time**

**September 24, 2018**

## SP Robot Study

### **1. Purpose:**

The purpose of this study is to evaluate the safety and feasibility of using the SP robot to perform single port robotic colon resection and transanal robotic surgery. The hypothesis of the study is that the SP robot will prove a safe effective modality to perform these procedures.

### **2. Subject Recruitment and Selection:**

The goal of the study will be to recruit 200 patients between the ages of 18 and 95 years of age, either male or female. Exclusion criteria would include emergency surgery and an inability to offer informed consent. There will be no inducement to the patients, pregnant women would be excluded as well.

### **4. Background:**

Minimally invasive colorectal surgery was first described in 1991 and has been adopted steadily in the United States in the ensuing 25 years. Offshoots of a laparoscopic approach in a multiport fashion has led to the development of the single port colorectal surgery first described in 2008 performed by, Lankenau trained fellow, [name]. Robotic surgery has been utilized for a full spectrum of abdominal surgery being performed. In the colorectal arena, the robotic approach for benign and malignant

disease is well established, with a great deal of literature generated regarding the safety and benefits of a colorectal robotic approach for benign and malignant disease. The section of colorectal surgery at the Lankenau Medical Center has been an active and robust contributor to surgical literature on laparoscopic surgery, robotic colorectal surgery, and single port laparoscopic surgery. Its one investigator has been involved in the development of clinical applications to the single port robotic platform where this has been utilized in cadaver work that has been published. Recently, the SP robot has gone through FDA clearance and is now available for clinical utilization. The FDA approval is for urologic surgery. The SP robot will be utilized in the same fashion to perform the same colorectal operations that we have been performing with multiple port placements in the past to accomplish robotic surgery in a single port platform in the colorectal arena. The principal investigator has worked on the SP robot over the past 3 years with extensive cadaver experience to develop its safe application in the colorectal field. This study will entail a collection of demographics, preoperative, perioperative and postoperative outcomes of the patients into a database to follow this, report on the outcomes, and notably answer questions to demonstrate the feasibility and safety of this approach in colorectal patients.

## **5. Research:**

All patients being considered for minimally invasive colorectal surgery will be evaluated for participation in the above study. The original goal will be 200 patients. All of these patients will undergo a standard minimally invasive resection in the same fashion as would be carried out with multiport laparoscopic or robotic surgery. The difference being that the operation would be performed with the single port robot as opposed to multiport robotic or laparoscopic surgery or single port-laparoscopic surgery. The exact same standard of operative care will be employed with these patients. Additional laparoscopic

ports would be utilized as needed to carry out the operation safely at the discretion of the principal investigator. The original target would be for 200 patients, this will then be continued based upon findings, safety and efficacy of this approach, and improved data in the database for further analysis. A preliminary safety analysis will be performed after 10, 20, and 40 patients and shared with the IRB to confirm the safety of this approach. Preoperative demographic information will be collected as well as perioperative outcomes and postoperative outcomes. Any preoperative data will include data related to age, gender, disease state, anatomic location, BMI, ASA classification, previous surgery and previous radiation therapy. The operative data will include time of surgery, total operative time, blood loss, disposable instrumentation utilized, cost data, assistants in the case, robotic console time, complications, IV fluids, blood transfusions, estimated blood loss, urine output, type of anastomosis, how the anastomosis was performed, and conversion rate to multiport surgery. In order to gauge the effect of the surgery on patients' quality of life, the following questionnaires will be administered pre-operatively and post-operatively: SF-36 and QoR-40. Because a validated survey for patient reporting of scarring outcomes does not currently exist, a comprehensive survey (known as the Patient Scar Assessment Questionnaire, PSAQ) whose validity and reliability has been reviewed will be utilized. A photo-series questionnaire, modeled after Dunker et al.'s widely used survey will also be used to help evaluate the cosmetic consequences of scarring and patient's preferences for future surgical approaches (open, laparoscopic, or single port).

Patients will be monitored for postoperative pain requirements (we will measure the total amount of narcotics used postoperatively per day), postoperative pain score, time to tolerating clear liquids, time to tolerating solid food, time to flatus, time to defecation, time to discharge, readmission rates will be tracked, as well as short term perioperative complications for 30 days or less. All these data will be compared to those from multiport

laparoscopic cases from previously published studies. Post-operative complication rates will be compared using the t-test. Subject data will be stored for the length of the IRB approved study and if we wish to continue using the data another IRB protocol will be submitted for approval. As an ongoing adjunct to this study long term complications including bowel obstruction, hernia rate and anastomotic problems will be noted. These data points will be noted for the length of the study, and we will seek another IRB approval to get longer term outcomes.

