## **6. Risk Assessments to the Patient:**

The risk to the patient would be the same as one with undergoing any major colorectal resection. This would include bleeding, infection, injury to other organs, bladder dysfunction, sexual dysfunction, the need for temporary stoma, permanent stoma and even death. These are inherent to this form of surgery represent the same risks done in an open, multiport laparoscopic, single port laparoscopic, or multiport robotic fashion. However this is the first time an SP robot will be used in humans for colorectal procedures. As such different complications rates may be encountered. Possible benefits to the subject would include decreased pain from less incisions and improved cosmesis with only one incision. Other potential benefits which have been seen in the single port literature have been decreased operative time, reduced blood loss, and a lower hernia rate. It does not seem to be any inherent risk singularly attributable to this robotic approach that would not be ongoing with other standard approaches currently employed. Potential risks would be minimized by the ability to add additional laparoscopic ports in the situation where adequate progress was not being achieved in a robotic single port fashion.

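### The protocol fixes published multiport laparoscopic cases as the comparator for every outcome, so transanal cases have no like-for-like benchmark

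*Protocol*

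**What the plan says.** Section 1 states that the study evaluates "using the SP robot to perform single port robotic colon resection and transanal robotic surgery". Section 2 gives one recruitment target for both: "The goal of the study will be to recruit 200 patients". No number per procedure appears anywhere.

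Section 5 lists the postoperative outcomes (pain, recovery of bowel function, discharge, readmission, 30-day complications) and then fixes the comparator: "All these data will be compared to those from multiport" "laparoscopic cases from previously published studies", citing references 10 to 13. The next sentence fixes the test: "Post-operative complication rates will be compared using the t-test".

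Two other places describe all patients in resection terms. Section 5 says "All of these patients will undergo a standard minimally invasive resection in the same fashion" as multiport surgery, and Section 6 says "The risk to the patient would be the same as one with undergoing any major colorectal resection". Neither says where transanal cases fit. The preoperative data items in Section 5 are "age, gender, disease state, anatomic location, BMI, ASA classification, previous surgery and previous radiation therapy". The operative items that follow include details of the anastomosis but not the procedure performed.

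**The concern.** The comparator is defined as multiport laparoscopic cases, a category of abdominal access, and its named sources are colonic or ileocaecal by title. One of the two procedures in scope does not fit it. If the outcomes of all 200 patients are set against these sources, a difference from the published rates, or the lack of one, may reflect the share of transanal cases and not the robot.

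The error can go either way. If transanal cases carry less risk than the benchmark resections, the robot looks too safe and an excess of complications in colon resections can be masked. If they carry more risk, the robot looks too dangerous. Section 6 describes this as the first human use of the device for colorectal procedures and allows that complication rates may differ, so the safety comparison is the part of the study that most needs to be interpretable.

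**Working it through.** **Scope against comparator.** The plan has no figure of its own to reproduce on this point: it states no rates, margin, power or significance level. The first check is therefore of the text.

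| Source | Subject, by title | Role in the protocol | Transanal? |
|---|---|---|---|
| Ref. 10 | Right colectomy, meta-analysis | Comparator | No |
| Ref. 11 | Colectomy for colon cancer, meta-analysis | Comparator | No |
| Ref. 12 | Ileocaecal resection in Crohn's disease | Comparator | No |
| Ref. 13 | Approaches to colon cancer | Comparator | No |
| Ref. 1 | Robotic transanal surgery in cadavers | Background only | Yes, but no patients |

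None of the 4 comparator references is transanal by title. Of all 16 citations, 1 is, and it cannot give patient outcome rates.

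**Possible size if the series is compared as a whole.** All rates, shares and published sample sizes below are assumptions, and no true robot effect is assumed. Let pc be the resection rate (also the benchmark), pt the transanal rate and s the transanal share. Then pooled rate = (1 − s)·pc + s·pt, and its distance from the benchmark is s·(pt − pc).

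- Lower-risk transanal cases (pc 20–25%, pt 8–10%, s 20–50%): the smallest gap is 0.2 × (0.20 − 0.10) = 2.0 points below the benchmark, the largest 0.5 × (0.25 − 0.08) = 8.5 points below.
- Higher-risk transanal cases (pt 30–40%, same pc and s): the smallest gap is 0.2 × (0.30 − 0.25) = 1.0 point above, the largest 0.5 × (0.40 − 0.20) = 10.0 points above.

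**Chance of a false conclusion.** These are exact binomial probabilities for n = 200 with a two-sided 5% t-test (the level is assumed). The first test treats the benchmark as a fixed 25%. The second is a two-sample test against 200, 500 or 1,000 published cases with a true rate of 25%. The share is s = 30%.

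| Transanal rate | Pooled rate | False conclusion | Fixed 25% | Two-sample, 200 / 500 / 1,000 |
|---|---|---|---|---|
| 10% | 0.7 × 25% + 0.3 × 10% = 20.5% | Robot safer | 33.6% | 18.8% / 23.7% / 26.5% |
| 40% | 0.7 × 25% + 0.3 × 40% = 29.5% | Robot worse | 29.1% | 17.1% / 23.4% / 27.0% |

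The nominal value is 2.5% in each direction. Drawing 140 resections and 60 transanal cases separately changes each probability by less than 0.5 points.

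**What a pooled 25% could conceal**, at s = 30%: the resection rate is (0.25 − 0.3 × 0.10)/0.7 = 31.4% if transanal cases run at 10%, or (0.25 − 0.3 × 0.40)/0.7 = 18.6% if they run at 40%.

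**The case against.** The strongest reply is that pooling is inferred. The comparator sentence follows a list of outcome variables and says which variables are compared. It does not say that the procedures are merged into one rate. A split by procedure could be made in a statistical analysis plan, which is not shown. This stands in part: the bias figures apply only if the series is compared as a whole. But the protocol provides no split, and with a split the transanal cases would still be set against multiport laparoscopic cases.

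Second, if the transanal cases are resections done through transanal access, as the resection wording in Sections 5 and 6 might suggest, multiport resection could be a defensible comparison of techniques. The protocol does not settle this. Even on that reading, the cited titles are colonic or ileocaecal.

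Third, the content of reference 13 cannot be checked from its title. That is true, but the comparator is defined as multiport laparoscopic whatever that review contains.

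Fourth, the illustration is a mid-range case. At the mild end the effect is small. With resection 20%, transanal 10% and a 20% share, a two-sample test against 200 to 500 published cases calls the robot safer about 7–8% of the time. With resection 25%, transanal 30% and a 20% share, it calls the robot worse about 4% of the time against 200 cases. At shares of 5–10% with rates of 25% and 10%, the figure is about 4–8%. This stands, and the larger figures should be read as possible, not as measured.

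Finally, the aim is safety and feasibility, and the literature comparison is not tied to the reviews after 10, 20 and 40 patients or to any decision rule. That limits the consequence, but the protocol still commits to a comparative test of complication rates.

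**Conclusion.** The concern holds and should be fixed. The mismatch between scope and comparator is certain from the text: transanal surgery is in scope, and the single comparator named is multiport laparoscopic, from sources that are colonic or ileocaecal by title. It does not depend on pooling or on the exact meaning of transanal.

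The size of the effect is not known. It is conditional on a whole-series comparison and on assumed rates and shares. Over the ranges of 20–50% share used here, the pooled rate lies from 8.5 points below to 10.0 points above the resection benchmark with no robot effect at all. At small shares the distortion is minor.

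**What to change.** Add to Section 5 of the protocol:

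> Colon resections and transanal procedures will be analysed and reported separately. Comparison with the published multiport laparoscopic cases (references 10 to 13) will be limited to colon resections, by resection type and disease where the published rates allow. Transanal procedures will be reported descriptively, or against published transanal series named in advance.

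Add the procedure performed to the listed operative data. Disease state and anatomic location are already collected and support the finer breakdown, but they do not identify the access route. Reconcile the resection wording in Section 5 with the transanal procedures in Section 1, so that it is clear what the transanal cases are.

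The cost is protocol wording, one data item and separate tables. A short literature search is needed only if a transanal comparison is wanted. The price is precision. At the assumed 30% share (0.3 × 200 = 60 transanal, 140 resections), a 25% rate has an exact 95% interval of 18–33% with 140 resections, against 19–32% with 200. A 10% rate has an interval of 4–21% with 60 transanal cases. The loss for resections is small. The transanal interval is wide.

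### The protocol states a safety-and-effectiveness hypothesis and compares all its data with published results, but names no primary outcome and no criterion that could refute it

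*Protocol*

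**What the plan says.** Protocol Section 1 gives the aim: "The purpose of this study is to evaluate the safety and feasibility of using the SP robot". It then adds a claim to be shown: "The hypothesis of the study is that the SP robot will prove a safe effective modality to perform these procedures".

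Protocol Section 5 lists what is collected. The operative list opens with "time of surgery, total operative time, blood loss, disposable instrumentation utilized, cost data, assistants in the case, robotic console time" and ends with the rate of conversion to multiport surgery. Two quality-of-life instruments follow ("the following questionnaires will be administered pre-operatively and post-operatively: SF-36 and QoR-40"), then a scar questionnaire and a photo-series questionnaire. The postoperative list covers narcotic use, pain score, five recovery or discharge times, readmission and 30-day complications. The analysis rule comes directly after it: "All these data will be compared to those from multiport" laparoscopic cases in earlier publications. One test is named, a t-test, for postoperative complication rates only.

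On size and monitoring, Section 5 says "The original goal will be 200 patients" and that "this will then be continued based upon findings, safety and efficacy of this approach". It also says "A preliminary safety analysis will be performed after 10, 20, and 40 patients", with the results going to the IRB.

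No section available to us calls any outcome primary, ranks the outcomes, or gives a margin, threshold or rule for calling the approach safe, effective or feasible.

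**The concern.** Which outcome answers the study question, and what result would count against the hypothesis, are design decisions that belong in the protocol. Here the protocol fixes a comparison rule that gives the outcomes equal standing and attaches no criterion to any of them. Three things follow.

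- **No result refutes the hypothesis.** Nothing says what complication rate would be too high, or what conversion rate would make the approach infeasible.
- **The supporting outcome can be chosen after the data are seen.** With many outcomes of equal rank, chance alone makes some favourable difference likely.
- **Absence of significance can pass for safety.** With no margin, a non-significant difference in complications could be reported as showing that the approach is safe.

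The protocol's risk section says that this is the first human use of the device for colorectal procedures and that complication rates may differ. Recruitment beyond 200 also depends on a judgement of safety and efficacy, so the undefined criterion affects how many patients are exposed.

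**Working it through.** The protocol states no alpha, power, margin or expected rate, so there is no planned figure to reproduce. The check counts the outcomes and shows what equal standing implies.

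**Count (Section 5)**

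- Operative items: 15
- Questionnaires: 4
- Postoperative items: 9
- Broad reading, everything collected during and after surgery: 15 + 4 + 9 = 28
- Narrow reading, only the postoperative list directly before the comparison sentence: 9
- Intermediate reading: dropping two near-duplicates (the two blood-loss items and the two operating-time items) leaves 28 − 2 = 26. Dropping console time and conversion to multiport, which have no clear counterpart in multiport laparoscopy, leaves 26 − 2 = 24.

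The three long-term items (obstruction, hernia, anastomotic problems) come after the comparison sentence and are not counted.

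**Chance of at least one spurious favourable result**

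Assume no true difference and each comparison tested at two-sided 5%, that is 2.5% in the favourable direction. Under independence the chance for k comparisons is 1 − 0.975^k:

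- k = 1: 2.5%
- k = 9: 1 − 0.7962 = 20.4%
- k = 24: 1 − 0.5446 = 45.5%
- k = 28: 1 − 0.4922 = 50.8%

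Recovery times, diet and discharge move together, so independence gives an upper figure. A simulation of 100,000 runs drew k standard normal statistics with equal pairwise correlation and counted the runs in which at least one exceeded 1.96:

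| Correlation | k = 9 | k = 28 |
|---|---|---|
| 0.3 | 16.5% | 33.6% |
| 0.5 | 13.5% | 24.6% |
| 0.7 | 10.1% | 16.5% |

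Across these readings and correlations the figure is at least four times 2.5% (10.1 / 2.5 = 4.0).

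**Reading non-significance as safety**

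The figures above do not capture this. Treat the published rate as fixed and take 200 patients. The 95% half-width for a proportion p is 1.96 × √(p(1 − p)/200). No complication rate is given, so p is assumed over a range:

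- p = 5%: 3.0 percentage points
- p = 10%: 4.2 points
- p = 20%: 5.5 points
- p = 30%: 6.4 points

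An observed excess over the published rate smaller than this would ordinarily not be significant. Without a margin, the protocol does not say whether such an excess is acceptable.

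**The case against.** The best defence is that this is a feasibility series feeding a database, that comparing can mean describing, and that safety is in practice judged on complications. They have the only named test, the early analyses after 10, 20 and 40 patients concern safety, and the risk section singles out complication rates.

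Much of this stands. It is too strong to say that the protocol has no safety outcome in view, and nothing in the text supports using a recovery time to demonstrate safety. No alpha is stated and nothing says the other outcomes will be significance-tested, so any family-wise error rate is illustrative.

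The count is also open. A reader might infer 20 or more significance tests and a false-positive chance of 37% (k = 9) to 76% (k = 28). The documents do not support that as the size of the problem. The comparison sentence directly follows a list of 9 items. Several operative items describe the case or have no laparoscopic counterpart, and the quality-of-life instruments are given before and after surgery, which suggests a within-patient purpose. Those percentages are also two-sided, so they count unfavourable results that could not be offered as support, and they assume independence.

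What does not stand is that complications are therefore the primary outcome. The protocol never says so. Complications appear in both the operative and the postoperative lists with no severity level, and the early safety analyses carry no criterion. Nothing plays even this implicit role for effectiveness or feasibility. A purely descriptive series would also not need a hypothesis, a named test and a commitment to external comparison.

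**Conclusion.** The point holds in this form: the protocol states a hypothesis but designates no primary outcome and no success criterion, so no result is identified that would refute it. This does not depend on how many outcomes the comparison sentence covers.

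The multiplicity is secondary and illustrative. The chance of at least one spurious favourable result is about 20% (9 outcomes) to 51% (28 outcomes) under independence, or about 14% to 25% at correlation 0.5, against 2.5% for one designated outcome. These figures assume that every comparison is tested at two-sided 5%, which the protocol does not state. For a safety claim, the missing margin matters more than the number of comparisons.

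The conclusion covers only the text at hand. Section 3 of the protocol was not available and could not be checked.

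**What to change.** In Sections 1 and 5, designate two outcomes from data already collected:

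- **Primary safety outcome:** the proportion of patients with any 30-day complication at or above a named grade on a stated severity scale. No scale appears in the text available, so it must be named.
- **Primary feasibility outcome:** the proportion of procedures completed without conversion to multiport surgery. State how additional laparoscopic ports, which the protocol allows, are counted.

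Estimate each with an exact 95% CI and judge it against a criterion that the sponsor fixes and justifies before enrolment. Say whether both criteria must be met for the hypothesis to be supported; if so, having two outcomes needs no alpha adjustment. Report colon resection and transanal procedures separately as well as together.

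Replace the sentence beginning "All these data will be compared to those from multiport" with one saying that all other outcomes are reported descriptively with CIs alongside published figures and support no claim of benefit.

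The cost is a short protocol revision: two definitions, a grading scale, a counting rule and two justified criteria. No extra patients are needed, and the only added recording is the complication grade, if it is not already captured. The downside is that the sponsor gives up inferential claims on the other outcomes.

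### The protocol fixes a t-test, a test for means, to compare yes/no complication rates with published series

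*Protocol*

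**What the plan says.** Section 5 (Research) follows patients for "short term perioperative complications for 30 days or less", among other outcomes. There is no concurrent control arm. The lead-in is "All these data will be compared to those from multiport" and the comparator is "laparoscopic cases from previously published studies". For complications it then fixes the method: "Post-operative complication rates will be compared using the t-test". This is the only statistical test the protocol names.

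The planned size is given as "The original goal will be 200 patients". The protocol does not state the form of the t-test (one-sample or two-sample, pooled or Welch), the significance level, the expected complication rate or the size of the published group.

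Section 1 gives the aim: "The purpose of this study is to evaluate the safety and feasibility of using the SP robot". Section 6, noting first human colorectal use of the device, adds: "As such different complications rates may be encountered".

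**The concern.** A complication rate, on its ordinary reading, is the share of patients with the event, and each patient contributes a 0 or a 1. The variance of such data is tied to the rate itself. A t-test ignores that link and estimates the standard error from the observed 0/1 values. If few events happen to be seen, the estimated standard error is too small and a low rate looks more convincing than it is. If many are seen, it is too large and an excess looks less convincing than it is.

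Safety is the stated purpose, and the protocol itself allows that rates may differ with this device. The one test it names should not make an excess of an uncommon complication harder to see, or a false finding of fewer complications more likely. Whether it does so depends on a choice the sentence leaves open.

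**Working it through.** The protocol has no figure of its own to reproduce here. The check compares the named test with tests for proportions.

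**Inputs.** From the protocol: 200 SP patients and a published comparator. Assumed, because the protocol is silent: two-sided 5% level (2.5% per tail), true rates from 1% to 30%, and published groups of 50 to 1000 patients or a fixed published rate. All error rates come from full enumeration of the binomial outcomes, with no simulation. Zero events give the one-sample t zero variance and are counted as no verdict.

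**1. One-sample t against a fixed published rate p0.** With x events, p̂ = x/200, s² = p̂(1 − p̂)·200/199 and t = (p̂ − p0)/√(s²/200) on 199 df.

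For p0 = 5%, the standard error implied by that rate is √(0.05 × 0.95/200) = 0.0154. The t-test uses 0.0111 at 5 events and 0.0203 at 18 events.

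- Worked count, 5/200: t = (0.025 − 0.05)/0.01107 = −2.26, p = 0.025. The exact binomial test gives p = 0.140.
- Cut-offs: t calls 'lower' at 1–5 events and 'higher' from 19. Exact binomial does so at 0–3 and from 17.

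| True rate | t: false 'lower' | t: false 'higher' |
|---|---|---|
| 1% | 0.0% | 0.1% |
| 2% | 7.2% | 0.3% |
| 5% | 6.2% | 0.6% |
| 10% | 5.7% | 1.6% |
| 20% | 4.3% | 1.6% |
| 25% | 2.8% | 2.3% |
| 30% | 3.6% | 2.0% |

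At 5% the exact binomial test gives 0.9% / 2.4%. At a 1% rate the chance of zero events is 0.99^200 = 13.4%. The test then has no value, and what is lost is the ability to see harm.

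Power for a true rise from 5% to 10% is 63% (t) against 79% (exact binomial). For 10% to 20% it is 97% against 97–98%, so the loss there is immaterial.

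**2. Two-sample t, 200 SP patients against N published, true rate 5% in both.**

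| N | Welch: false 'lower' / 'higher' |
|---|---|
| 50 | 0.5% / 9.2% |
| 100 | 1.4% / 4.7% |
| 200 | 2.4% / 2.4% |
| 300 | 3.2% / 1.7% |
| 1000 | 5.1% / 1.2% |

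The pooled t-test against N = 1000 gives 1.8% / 3.1%, the same as chi-square.

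Power for 10% against a published 5%, Welch and chi-square respectively:
- N = 1000: 61% and 74%.
- N = 200: 47% and 47%.
- N = 100: 39% and 29%. Here the higher Welch figure is bought with the inflated 'higher' error above.

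**3. Worked counts against 50/1000.**

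- 18/200: difference 0.04. The Welch standard error is √(0.0823/200 + 0.0475/1000) = 0.0214, so t = 1.87 and p = 0.063. Chi-square uses the pooled rate 68/1200 = 0.0567, standard error √(0.0567 × 0.9433 × (1/200 + 1/1000)) = 0.0179, z = 2.23, p = 0.026. Fisher gives 0.042. Welch misses an excess that both proportion tests flag.
- 4/200: Welch p = 0.013, chi-square 0.062, Fisher 0.063. Welch declares a reduction that neither proportion test supports.

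**The case against.** The strongest reply is that a plain reference to the t-test for two groups most naturally means Student's pooled test. On 0/1 data that test returns practically the same verdicts as chi-square at every published size checked, so the harm would be nil. This is correct for that form. But the protocol does not say which form it means, and a comparison with published results invites a one-sample test against a quoted rate, or a Welch test against a group of another size.

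Second, the effect shrinks at higher rates. For Welch against 1000 it is 3.4% / 1.7% at a 15% rate and 3.2% / 1.9% at 20%. That stands: the distortion matters mainly for uncommon complications. The result at very low rates also depends on how zero events are handled. If they were counted as 'lower', the 2% row would read 8.9% instead of 7.2%, and the 1% row 13.4% instead of 0.0%.

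Third, the protocol does not define the rate. If it meant the mean number of complications per patient, a t-test could be defended. The text does not say so, and a two-sample test would then need standard deviations from the published reports.

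Fourth, no sample size, margin or stopping rule rests on this test, and the early looks ("A preliminary safety analysis will be performed after 10, 20, and 40 patients") are not tied to it. That stands and limits the severity. A statistical analysis plan might specify a different test, but the protocol states this one positively, so it is a choice made and not a detail left open.

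**Conclusion.** The concern holds. The protocol names a method for means for an outcome that is a proportion, and nothing elsewhere in it corrects this. It should be fixed, but it does not invalidate the study.

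The consequence is conditional on the form of the test:

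- **One-sample t:** at an assumed 5% rate and 200 patients, false 'fewer complications' is 6.2% and false 'more' is 0.6%. Power for a doubling to 10% falls from 79% to 63%. The lean is clear from about 2% to 20% and small at 25% to 30%.
- **Welch t:** it leans toward 'fewer' when the published group is larger than 200, has no lean at equal size, and leans toward 'more' when it is smaller.
- **Pooled t:** no practical difference from chi-square.

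These sizes rest on the assumed rates, published group sizes and 5% level. That the named test does not suit the outcome does not rest on them. The effect is confined to the reported safety comparison.

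**What to change.** Replace the t-test sentence in section 5 with wording such as:

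> The proportion of patients with at least one complication within 30 days will be reported with an exact (Clopper-Pearson) 95% confidence interval. It will be compared with published numerators and denominators by a chi-square (score) test, with a 95% confidence interval for the difference in proportions. Where only a published rate is available, an exact binomial test against that rate will be used.

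The cost is one sentence, with no extra patients or data. The wording also makes the patient-level reading of the rate explicit, which the sponsor should confirm is intended.

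Two limits remain. Chi-square is itself uneven when very few events are expected: at a 1% rate with 200 against 100 patients it gives 4.1% / 0.04%, no worse than the pooled t. The change also does not settle how comparable the published series are with these patients, or how several published sources would be combined.
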